5.1.6 Interim Analyses

No interim analysis will be performed.

5.2 Determination of Sample Size

The sample size assumptions and estimate are summarized as follows:

Table 5-4 **Sample Size Assumptions**

Parameter	Assumption / Estimate
Primary endpoint	Chin retraction assessment responder
Risk difference ¹	40 (80% Voluma vs 40% Control)
SD	NA
α	5%
Sides	2
Power	>99%
N per group	120 in Voluma group, 40 in control group
Screen Fail Rate	15%
Drop-out Rate	15%
N total	224

¹ Based on literature/previous study VOLUMA-002 and relevant details.

5.3 Changes in the Conduct of the Study or Planned Analyses

Prior to database lock, there were no changes in study conduct or planned analyses (except per protocol analysis) from what was described in the protocol and detailed in the SAP. No unplanned analyses were conducted, and the planned analyses were conducted following database lock.

6. Data Handling and Analysis Conventions

6.1 Analysis Days

Treatment Day for effectiveness, [REDACTED] and AE are defined as follows:

Table 6-1 Analysis Day Definitions

Term	Description
Effectiveness [REDACTED] Effectiveness Day	Treatment Group and Control Group (only the control subjects receiving optional treatment): Relative to the last treatment date (either the initial treatment, if no touch-up is performed, or the touch-up treatment) 
○ Effectiveness Day = analysis date – last treatment start date + 1○ Effectiveness Day 1 = last treatment start date Control (before receiving optional treatment): Relative to the randomization date 
○ Effectiveness Day = analysis date – randomization date +1○ Effectiveness Day 1 = randomization date
Safety (including AE [REDACTED] Safety Day)	Treatment Group and Treated Control (i.e., only the control subjects receiving optional treatment): Relative to treatment date (initial and touch-up) Safety Day = analysis date – initial treatment date + 1 Safety Day 1 = initial treatment date Control (before receiving optional treatment): Relative to the randomization date 
○ Safety Day = analysis date – randomization date +1○ Safety Day 1 = randomization date Treatment Group Only: Relative to the repeat treatment date (after repeat treatment) Safety Day = analysis date – repeat treatment date + 1 Safety Day 1 = repeat treatment date

6.2 Analysis Visit Windows

All scheduled and unscheduled visits with complete dates will be assigned visit windows and used for analysis. However, if a scheduled visit with incomplete date is available with no other visits with complete date during the visit window, then the visit with incomplete date may be used for analysis and the nominal visit will be used as the visit window (e.g., if the only assessment collected for Month 6 visit window is on a Month 6 CRF with incomplete date, then those data will be used for the Month 6 assessments).

[figure not shown]
If there are multiple visits occurring within a single visit window with relevant data, the visit closest to the target day will be used in the analysis of the corresponding visit windows. If 2

[figure not shown]
visits are equal distance to the target day and are the same type of visit, then the later visit will be used.

Analysis visit windows for effectiveness endpoints and safety are defined as follows:

6.2.1 Effectiveness

The analysis visit windows for effectiveness endpoints are defined as follows:

6.2.2 Safety

No analysis visit windows are required for TEAEs [REDACTED]. Analysis visit windows will only be used for summarizing [REDACTED]. For the treatment group, refer to table 6.2 for analysis visit windows [REDACTED]. For the control group in the control period (i.e., no treatment period) refer to table 6.3 and for the control group in the treatment period refer to table 6.2.

6.3 Missing/Incomplete Date Conventions

6.3.1 Missing/Incomplete AE Start Date

Imputation of dates with missing day and/or month is only applied to TEAEs. If adequate information is available, no imputation is needed. TEAE start dates with missing day or month will be imputed as following:

- If day and month are missing but year is available, then the imputed day and month will be 01 Jan or the initial treatment date if they have the same year, whichever is later (because TEAE onset is not expected prior to administration of study treatment)
- If day is missing but the month and year are available, then the imputed day will be the first day of the month or the initial injection date if they have the same month and year, whichever is later

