11.1 Definitions

11.1.1 Adverse Event

An AE is defined in accordance with ISO 14155 as “any untoward medical occurrence, unintended disease or injury, or untoward clinical signs (including abnormal laboratory findings) in subjects, users, or other persons, whether or not related to the investigational medical device.” This definition includes events related to the investigational medical device or comparator and events related to the procedures involved except for events in users or other persons, which only include events related to investigational medical devices.

Disease signs and symptoms that existed prior to the study treatment are not considered AEs unless the condition recurs after the subject has recovered from the pre-existing condition or the condition worsens in intensity or frequency during the study.

AEs will be monitored throughout the study beginning with signing of the ICF. At each postscreening visit, the TI (or designee) will begin querying for AEs by asking each subject a general, non-directed question such as “Have you had any changes to your condition since your last visit?” Previous AEs and changes in therapy/concomitant medications are to be updated. Directed questioning and examination will then be done as appropriate. All reportable AEs and clinically significant abnormal laboratory findings will be documented on the appropriate eCRF.

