5.1.4.2 Adverse Events

The following adverse event (AE) terms are defined:

Table 5-18 AE Terms

Term	Description
Treatment-emergent	Treatment group: An event that initially occurs or increases in severity on or after the treatment start date.
Adverse Event (TEAE)	Control group: An event that initially occurs or increases in severity on or after randomization date.

AEs and encompassing abnormalities, reported as occurring after the Screening Visit, will be coded using MedDRA version 18.1 or newer. A listing for all TEAEs in the treatment and control groups will be presented. Additionally, unique subjects reporting AEs as well as the number of events in the following AE categories will be summarized for treatment subjects, control subjects after optional treatment, and all treated subjects as follows:

Table 5-3 AE Summaries

Endpoint	Description	Timing	Methodology
Overall summary	Overall summary only for the following categories: 
 • Treatment-emergent AEs (TEAEs) • Treatment-related TEAEs • Treatment-related TEAEs at injection site • Treatment-related TEAEs not at injection site • All Serious AEs (SAE) • Treatment-related SAE • Discontinued due to TEAE • Deaths 	Treatment period	Categorical counts, Event descriptives
TEAEs	
 • Overall summary and by SOC, PT and severity 	Treatment period	Categorical counts, Event descriptives
Treatment-related TEAEs	
 • Overall summary and by SOC, PT and severity • Overall summary by severity, duration, time to onset, resolution, and treatment required 	Treatment period	Categorical counts, Event descriptives
SAEs	Overall summary and by PT	Treatment Period	Listing
AEs leading to discontinuation	Overall summary and by PT	Treatment Period	Listing

[figure not shown]
Note: SOCs will be sorted alphabetically; PTs will be sorted in descending frequency in the treatment group. AEs for control group before and after optional treatment are summarized separately.

[figure not shown]
Time to onset for TEAEs will be computed as

AE start date - reference date + 1,

where, the reference date is initial treatment date for TEAEs occurring on or after initial treatment but before touch-up treatment and the reference date is touch-up treatment date for TEAEs occurring on or after touch-up treatment but before repeat treatment.

Duration for TEAEs will be computed as AE end date – AE start date + 1.

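### The partial-date rule for TEAE onset can move a control-period event to the optional injection date, and so into the treated counts

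*SAP*

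**What the plan says.** SAP Table 5-18 (Section 5.1.4.2) sets a different start of TEAE counting for each arm. For controls it reads: "Control group: An event that initially occurs or increases in severity on or after randomization date". Protocol 4.2 gives controls 6 untreated months before optional treatment, so events in those months are TEAEs by definition.

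Section 5.1.4.2 then summarises AEs for "treatment subjects, control subjects after optional treatment, and all treated subjects", and a note to the AE summaries table adds: "AEs for control group before and after optional treatment are summarized separately".

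Section 6.3.1 covers partial TEAE start dates in both arms with one rule:

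- Day and month missing: "01 Jan or the initial treatment date if they have the same year, whichever is later", justified with the words "because TEAE onset is not expected prior to administration of study treatment".
- Day missing: "first day of the month or the initial injection date if they have the same month and year, whichever is later".

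A general sentence precedes both: "If adequate information is available, no imputation is needed". The SAP does not define what counts as adequate. Elsewhere it does take randomisation as the origin of the control period: in Table 5-10 for prior and concomitant medication, and in Table 6-1 for Safety Day.

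**The concern.** The reason given in 6.3.1 holds for events after treatment and contradicts Table 5-18 for events in the untreated control period. The rule has no branch for that period and no floor at randomisation. For a control who takes up optional treatment, the initial treatment date is the first optional injection (Table 6-1), about 6 months after TEAE counting began.

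At stake is which summary an event enters. An untreated-period event that is given the injection date looks like a post-injection event. It can be added both to the treated-control and to the all-treated TEAE counts, and be lost from the summary before optional treatment.

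**Working it through.** The plan states no figure on this point, so the check applies the rule literally and then asks how often it misplaces an event.

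**The rule.** With injection date I:

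- only the year known: imputed onset = later of 01 Jan and I if the years match, otherwise 01 Jan;
- only month and year known: imputed onset = later of the first of the month and I if month and year match, otherwise the first of the month.

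**Worked cases (invented dates).**

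| Randomised | True onset | Recorded as | Injected | Imputed onset |
|---|---|---|---|---|
| 10 Jan 2017 | 15 Mar 2017 | 2017 | 10 Jul 2017 | 10 Jul 2017 (post-treatment) |
| 20 Jan 2017 | 5 Jul 2017 | Jul 2017 | 20 Jul 2017 | 20 Jul 2017 (post-treatment) |
| 10 Sep 2016 | 15 Nov 2016 | Nov 2016 | 10 Mar 2017 | 01 Nov 2016 (control period, correct) |
| 10 Sep 2016 | 15 Nov 2016 | 2016 | 10 Mar 2017 | 01 Jan 2016 (before randomisation) |

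The rule for start dates is not capped at the event's end date. If the first event is known to have ended on 22 Mar 2017, the SAP's duration formula (end − start + 1) gives −110 + 1 = −109 days.

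**Share of control-period events imputed to the injection date, later-treated controls.** Assumptions: randomisation uniform over a calendar year, 183-day control period, onset uniform within it.

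- Year-only: the mean gap from onset to injection is 183 / 2 = 91.5 days. A year boundary falls in the gap with probability 91.5 / 365 = 0.25, so the share is 1 − 0.25 = 0.75.
- Day missing: about 15 days of the injection month precede the injection, so the share is 15 / 183 = 0.08.

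Simulation of 400,000 events per scenario gives 0.747 and 0.079. Complete enumeration with a 182-day period gives 0.749 and 0.081.

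**Sensitivity.**

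| Scenario | Year-only | Day missing |
|---|---|---|
| Control period 170 days | 0.766 | 0.087 |
| Control period 200 days | 0.725 | 0.074 |
| 9-month recruitment, assumed starts Jun 2016 to Mar 2017 | 0.664 to 0.914 | 0.079 to 0.082 |

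**Per 10 partial-date control-period events in later-treated controls.** With p the year-only share, the number imputed to the injection date is 10 × [p × 0.748 + (1 − p) × 0.080]:

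- p = 0: 0.8
- p = 0.1: 0.748 + 0.72 = 1.5
- p = 0.25: 1.87 + 0.60 = 2.5
- p = 1: 7.5

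In never-treated controls there is no injection date, so the number is 0.

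**Dates before randomisation.** In later-treated controls about 25% of year-only and 8% of day-missing dates are imputed to before randomisation; in never-treated controls about 75% and 8%. This is inconsistent with Table 5-18, but the event stays on the untreated side. A count changes only if TEAE status is re-derived from the imputed date.

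**What an end-date check would catch.** Share of the events moved to the injection date whose true end lies before it, for assumed durations:

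| Duration | Year-only | Day missing |
|---|---|---|
| 3 days | 0.986 | 0.871 |
| 7 days | 0.957 | 0.642 |
| 30 days | 0.798 | 0.001 |

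**Would randomisation as the floor for every control event do?** No. For genuine post-injection events over an assumed 210 days, that floor puts 0.712 of year-only dates (0.615 to 0.872 across recruitment windows) and 0.070 of day-missing dates into the untreated period. The present rule misplaces none of these.

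**The case against.** The strongest reply is that the SAP never says the imputed date decides the column. Only events already classed as TEAEs are imputed, so some placement from other information must come first, and the same information can place the event relative to the injection. AEs are sought throughout ("At each postscreening visit, the TI (or designee) will begin querying for AEs", Protocol 11.1.1) and recorded upon awareness (Protocol 11.2). A control-period event would therefore normally be on file by the injection visit, and the sentence on adequate information would then stop the imputation. The AE summaries are also timed to the treatment period, where the premise is right. Finally, the frequency of partial dates is unknown, the control group is small (up to 56 under the 224-subject plan), and the error goes against the device.

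Much of this stands as a limit on size. The percentages assume that the adequate-information sentence never operates, and they model neither reporting visits nor recording dates. Investigator causality judgement largely protects the treatment-related tables, and under Section 6.4 listings generally show the actual partial date.

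It does not remove the fault. Adequate information is undefined, and nothing says that the reporting visit or end date settles the period, so two programmers could produce different counts. The narrower treatment-period reading conflicts with the note that requires a separate control summary before optional treatment. The stated premise remains false for those events.

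**Conclusion.** The concern holds, as a minor point. Section 6.3.1 as written misdates some control-period TEAEs and can move them into the treated-control and all-treated summaries. The contradiction with Table 5-18 rests on the text alone.

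The size rests on assumptions: uniform randomisation and onset, a control period of about 183 days, and no use of other information to place the event. On these, about 8% (7 to 9%) of day-missing and about 75% (66 to 91%) of year-only control-period events in later-treated controls go to the injection date. The absolute number cannot be derived from the documents and is probably small. The effect is limited to all-causality TEAE counts, overstates them for treated subjects, and does not touch effectiveness.

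**What to change.** Amend SAP 6.3.1 so that, for control subjects:

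1. A partial-date event is first assigned to the control or the post-treatment period from the reporting visit, the known month or year, and the end date.
2. The floor is the randomisation date for control-period events and for never-treated controls, and the optional-treatment date for post-treatment events.
3. No start is imputed later than a known end date.
4. If the period cannot be determined in a later-treated control, the present post-treatment default is kept and the event is flagged.

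Randomisation should not become the floor for all control events, because that would misplace genuine post-injection events.

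The cost is two or three sentences and slight extra programming. The remaining drawback is that events of undeterminable period still count against the device, as they do now.

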6.3.2 Missing/Incomplete AE End Date

Imputation of dates with missing day and/or month is only applied to TEAEs. If adequate information is available, no imputation is needed. TEAE end dates with missing day or month will be imputed as following:

- If day and month are missing but year is available, then the imputed day and month will be 31 Dec or the study exitdate if they have the same year, whichever is earlier

If day is missing but the month and year are available, then the imputed day will be the last day of the month or the study exit date if they have the same month and year, whichever is earlier

6.4 Imputed Value Listing Conventions

In general, listings will present the actual partial or missing values rather than the imputed values that may be used in endpoint derivation. In instances where imputed values will be presented, imputed values will be flagged. Actual rules will be fully defined in the table, figure, and data listing specification document.

[figure not shown]
Appendix A: Allergan Chin Retrusion Scale

[figure not shown]
Table 1: Allergan Chin Retrusion Scale (ACRS)

Score	Grade	Description
0	None	No chin retrusion; Chin midpoint* at or in front of the lower vermillion border vertical line
1	Minimal	Minimal chin retrusion; Chin midpoint* is between the labiomental sulcus vertical line and lower vermillion border vertical line
2	Moderate	Moderate chin retrusion; Chin midpoint* at labiomental sulcus vertical line
3	Severe	Severe chin retrusion; Chin midpoint* slightly behind labiomental sulcus vertical line
4	Extreme	Extreme chin retrusion*; Chin midpoint significantly behind labiomental sulcus vertical line

* Chin midpoint: the midpoint between the labiomental sulcus and the inferior point of the chin

Figure 1: Lines Used in the ACRS Descriptions

ALLERGAN

Statistical Analysis Plan
